## 1. INTRODUCTION

Cerebral palsy (CP) is a movement and postural disorder due to lesion to immature brain. Spasticity is the most common movement disorder in children with cerebral palsy (CDC) and causes difficulty with walking, musculoskeletal complications such as hip dislocation, scoliosis and joint contracture, pain and balance issues (Balaban et al., 2012). Spastic muscles are stiff and weak (Campbell & Ball, 1978). A combination of spasticity and weakness in children with CP makes them walk difficult and less efficient. Spasticity management has been very important for children with CP for activity of daily living including walking (Massin & Allington, n.d.) Using botulinum toxin A (BoNT-A) injections to control spastic lower limbs became almost first line treatment for children with CP to improve gait, range of motion and quality of life. (Ade-Hall & Moore, 2000). Several studies reported that children with CP showed higher energy expenditure during walking compared to typically developing peers. (Balaban 2007 & Rose et al 1990 Steele K et al 2017) This increase is due to combination of the mechanical inefficiencies during ambulation caused by spasticity (Reddihough et al., 2002), muscle co-contraction ((Balaban et al., 2012), limited range of motion, muscle weakness and loss of balance (Norman, 2004). Perhaps, improving coordination of walking by reducing in spasticity with BoNT-A may improve energy expenditure by improving coordination of muscle activity which is related to peak power output (Wakeling et al, 2010). Energy expenditure is an objective measure of evaluating the energy cost required for movement (Rose et al., n.d.) Generally, the oxygen consumption (VO2) is used to measure energy expenditure and one of the most significant markers of aerobic fitness and endurance (*ACSM's Advanced Exercise Physiology*, 2006). The rate of oxygen consumption (mL/kg/min) was significantly higher in the children with diplegia than in those with hemiplegia or with spina bifida or the healthy children (Rose et al., n.d.). Oxygen cost (mL/kg/m) was significantly higher, and velocity was significantly slower in all the groups with disability than in the healthy children (Duffy and Graham 2014). Balaban et al showed that botulinum toxin A injections to spastic gastric muscles decreased VO2 and gait parameters at 2-month post injections. We hypothesized that BoNT-A injections to spastic lower limbs of ambulant spastic CP decrease energy expenditure during walking. The aim of this study is to investigate the effect of spasticity management using Dysport® (AbobotulinumtoxinA) on the walking efficiency, oxygen consumption and gross motor function and gait parameters of children with CP.

## 2. DESIGN

This study is a single center, open label study.

We seek to recruit 15 children diagnosed with Cerebral Palsy (CP) in order to determine the efficacy of single event multi level chemoneurolysis (SEMLC) with Dysport® on energy expenditure as measured by oxygen consumption (VO2) during the 6 minute walk test.

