## 2.1 Participants

All subjects will be recruited from [name] Physical Medicine & Rehabilitation clinic. [name] will approach eligible patients and their parents in order to explain the study and to determine interest. A researcher of the study team will email and/or telephone call eligible participants on behalf of [name] and with her permission to inform the parents of the eligible participant of the study.

Inclusion Criteria:

- Age: 5-17 years. *Must be <18 prior to injection.*
- >10 kilograms at screening and injection visits
- Diagnosis of spastic diplegia OR mild- to moderate spastic quadriplegia Cerebral Palsy
- Gross Motor Function Classification System level: I, II, III
- Ability to ambulate independently without aid, equinus gait
- Absent of joint or bone deformities
- Eligible to receive SEMLC
- Cooperative and tolerant to testing procedures during clinic screening
- Presence of spasticity in one or both legs
- Be on a stable dose and regimen if on any prescribed medication/s
- Parent must have signed written informed consent and the Patient Authorization for Use and Release of Health and Research Study Information

Exclusion Criteria:

- Ankle contractures no more than -10 degrees with the knee extended
- Hemiplegia
- Wheelchair dependent
- Received Botulinum toxin within previous 4 months
- Uncontrolled epilepsy or certain types of seizures
- Fracture in the study limb within previous 12 months
- Infection or skin disorder at planned injection site
- Shortness of breath or other respiratory issues
- Uncontrolled clinically significant medical condition
- Received phenol or alcohol block in the study limb within previous 6 months
- Surgery in the study limb within previous 12 months
- Serial casting within previous 12 months
- New physiotherapy and/or orthotic regimen <1 month before study start. (physiotherapy and/or orthotic regimen will be permitted if it began >1 month before study start and maintained throughout study)

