## 2.2 Outcome Measures

Primary Question: Does single event multi level chemoneurolysis (SEMLC) have an effect on energy expenditure and walking efficiency as measured by oxygen consumption (VO2) and gait parameters during the 6 minute walk test in 15 children diagnosed with cerebral palsy (CP)?

Hypothesis: If 15 children receive SEMLC, then energy expenditure (VO2) will decrease due to increased walking efficiency and gait parameters during the 6 minute walk test.

Secondary Question: Does SEMLC have an effect on 6 minute walking distance in 15 children diagnosed with CP?

Hypothesis: SEMLC will increase the distance walked during the 6 minute walk test.

Secondary Question: Does SEMLC have an effect on the Gross Motor Functional Classification System (GMFCS) classification in 15 children diagnosed with CP?

Hypothesis: SEMLC will decrease a child's GMFCS classification due to increased physical function.

Secondary Question: Does SEMLC have an effect on ankle muscle spasticity as measured by the Modified Ashworth Scale (MAS) and the modified Tardieu Scale?

Hypothesis: SEMLC will decrease ankle muscle spasticity and in turn improve MAS and modified Tardieu Scale scores.

Secondary Question: Does SEMLC have an effect on dynamic balance during walking in 15 children diagnosed with CP?

Hypothesis: SEMLC will increase dynamic balance during walking.

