## 2.3 Procedures

Baseline (within 1 week prior to Dysport® treatment):

Before initiating any study procedures the informed consent will be discussed and signed with the parent(s) of the participants and the researcher will answer any questions. If capable of providing assent (>7 years old), the participant will sign the assent form. Once the consent and assent forms are discussed and signed the following assessments will be performed: demographics, height, weight, calculated body mass index (BMI), Modified Ashworth Scale (MAS), modified Tardieu Scale, range of motion of major joints (i.e., hip, knee, ankle), the Cerebral Palsy Quality of Life Questionnaire (CP QOL) for Children (9-12 years) or Adolescents (13-18 years), and the CP QOL for caregivers, 6 minute walk test (with mobile oxygen consumption), and gait analysis.

Degree of spasticity/tone in the lower limbs will be measured by the Modified Ashworth scale while the participant is relaxed and in the supine position (1). If testing a muscle that primarily flexes the hip, knee, or ankle joint the investigator will place the joint in a maximally flexed position and move the joint to a position of maximal extension over one second. If testing a muscle that primarily extends the hip, knee, or ankle joint the investigator will place the

joint in a maximally extended position and move the joint to a position of maximal flexion over one second.

The Modified Tardieu Scale will be used to assess spasticity by measuring different angles of muscle reaction in response to a passive force (2). Two angles will be measured from each major joint (i.e., hip, knee, ankle): R1, the angle in which clonus was felt during a quick passive stretch of the muscle; R2, the angle of full passive range of motion. The difference between the two angles ( $R2 - R1$ ) will be recorded for each muscle group. The participant will be lying supine for all angle measurements.

Range of motion of the lower limbs (hip, knee, ankle) will be measured by passively moving the patient's joint to a point of resistance where then the joint angle will be measured by a goniometer. Hip flexion will be measured with the patient lying supine. Knee flexion and extension will be measured with the patient lying supine. Ankle dorsiflexion will be measured with the knee extended in the supine position. The Thomas Test will also be used to assess hip flexion with the patient lying in supine (3).

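### An uncontrolled before-after study of 15 treated children is given the objective of determining efficacy, which its design cannot deliver

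*Combined protocol and SAP*

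**What the plan says.** Section 2 describes the design in one sentence: "This study is a single center, open label study". It then gives the size and purpose: "We seek to recruit 15 children diagnosed with Cerebral Palsy (CP", recruited "in order to determine the efficacy of single event multi level chemoneurolysis (SEMLC", with oxygen consumption (VO2) during the 6-minute walk test as the measure. The Introduction is milder: "The aim of this study is to investigate the effect of spasticity management using Dysport".

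Section 2.2 puts the primary question causally: "Does single event multi level chemoneurolysis (SEMLC) have an effect on energy expenditure and walking efficiency". All five of its questions ask whether SEMLC has an effect. The primary hypothesis names the cause in advance: "Hypothesis: If 15 children receive SEMLC, then energy expenditure (VO2) will decrease due to increased walking efficiency".

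The visit list in Section 2 and the procedures in Section 2.3 give every child the same sequence. There is one baseline, "Baseline (within 1 week prior to Dysport® treatment", then injection, then the same tests at 4 and 12 weeks. The available text describes no control arm, randomisation, blinded assessor, untreated run-in, repeat baseline, practice walk or external comparator. It also contains no statistical analysis section and no statement of limitations.

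**The concern.** Efficacy is a comparison between what happened with treatment and what would have happened without it. This design observes only the first. Any change that the children share between baseline and follow-up enters the before-after difference in full, whatever its cause.

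The threats are not equally strong for VO2:

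- **Familiarisation** is the most direct. The only described accustoming to the mask is a three-minute rest before the walk.
- **Expectation** comes next. The walk is self-paced and treatment is open label, so belief in the treatment can alter pace and effort, and with them VO2 and distance.
- **Other change over time** across 12 weeks cannot be excluded, although its direction and size are unknown.

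At stake is what the study may conclude. With the objective as worded, a fall in VO2 answers the efficacy question affirmatively even if SEMLC contributed nothing to it.

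**Working it through.** **What each contrast contains.** Let Δ be the mean within-child change from baseline. Then Δ = treatment effect + non-treatment drift. All children are treated and there is one baseline, so the data give one estimate (Δ) for two unknowns. No analysis of these visits can separate them.

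**The plan's own figure.** The only design figure is 15 children. The documents give no alpha, power, effect size or SD, so it cannot be reproduced. What follows is illustration only.

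**Inputs.** n = 15 (Section 2). Assumed: a paired t-test, two-sided alpha of 0.05, a true treatment effect of zero, and drift of b SDs of the within-child change in the favourable direction (a fall in VO2).

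**Formula.** P(favourable significant result) = 1 − F(t; df, δ), where F is the noncentral t distribution function, df = n − 1 = 14, t = 2.145 and δ = b√n.

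| Assumed drift b (SD of change) | δ = b√15 | Favourable significant result |
|---|---|---|
| 0 | 0 | 2.5% |
| 0.25 | 0.97 | 14.5% |
| 0.50 | 1.94 | 43.8% |
| 0.75 | 2.90 | 77.1% |

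**Would more children help?** At b = 0.30 the same calculation gives 19% with n = 15, 55% with n = 50 and 84% with n = 100. A larger sample makes the error more likely, because it estimates treatment plus drift more precisely. The fault is the missing comparator, not the number 15.

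**How much could regression to the mean supply?** If baseline lies c SDs of a single measurement above the child's usual level, and test-retest reliability is ρ, the expected shift in SDs of the change is (1 − ρ)c / √(2(1 − ρ)). Take ρ = 0.6 to 0.9 (assumed).

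- For c = 0.5 the shift is 0.22 down to 0.11.
- For c = 1 it is 0.45 down to 0.22.
- To reach 0.50 by this route alone, c would have to be 0.50 × √0.8 / 0.4 = 1.1 at ρ = 0.6, or 0.50 × √0.2 / 0.1 = 2.2 at ρ = 0.9.

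Regression alone is therefore an unlikely source of the larger rows in the table. Those rows need substantial familiarisation or expectation drift, for which the documents give no figure.

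**The case against.** The plan standardises a good deal. Section 2.1 requires tolerance of the testing procedures at clinic screening, stable medication, and a physiotherapy and orthotic regimen that is established and maintained. Section 2.3 provides the mask rest and keeps shoes, orthoses and devices the same throughout. VO2 is measured by instrument, so it is less exposed to open-label bias than the Ashworth, Tardieu or quality-of-life scores. The design is openly declared, the Introduction's aim is milder, and asking whether a treatment has an effect is ordinary phrasing. All of this stands, and it lowers the likely drift. None of it shows the untreated course, and the Design section still says efficacy will be determined.

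Four stronger readings are tempting, and the documents do not support them:

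- **That a p-value below 0.05 will be reported as proof of efficacy.** No test, alpha or reporting rule appears in the available text. What can be said is that drift could not be told apart from a treatment effect.
- **That children are tested at a low point.** No entry criterion selects on VO2, energy cost or walking distance. The exclusion "Received Botulinum toxin within previous 4 months" works as a washout, and earlier toxin is not required for entry. Regression is more plausible for spasticity scores, since children enter when eligible for injection.
- **That growth biases the result.** Its direction and size over 4 to 12 weeks are not shown.
- **That the study is illegitimate without a control arm.** An uncontrolled exploratory study is sound if its claim matches its design.

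**Conclusion.** Wrong as written. Sections 2 and 2.2 set a causal objective that a single treated group with one baseline cannot meet. This conclusion rests on the visit structure alone and needs no numerical assumption.

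The size of the problem is unknown. The range of about 15% to 77% shows how sensitive the conclusion is to drift. It is not an estimate of this trial's error rate, and with no drift the favourable rate stays at 2.5%. The defect lies in the stated objective and the permitted inference. The measurements themselves are not in question here.

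**What to change.** In Sections 2 and 2.2, replace the wording about determining efficacy and having an effect with *estimate the change from baseline after* SEMLC, and bring the hypotheses into line. Then add a statement of this kind:

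*This study is exploratory. Results will be given as mean within-child change from baseline with 95% confidence intervals at 4 and 12 weeks. Because there is no comparator, the change will not be attributed to SEMLC.*

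The cost is wording only. The downside is a less favourable headline claim. Rewording leaves the data and the drift unchanged, but it settles beforehand what may be concluded from them.

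Two additions look attractive and are not recommended as remedies:

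- **A control arm at this size.** With a two-sided alpha of 0.05 and the normal approximation, splitting 15 children 1:1 (7.5 per arm on average) gives about 16%, 33% and 49% power for differences of 0.5, 0.78 and 1.0 SD. Reaching 80% would take 63, 26 and 16 children per arm.
- **Correlating change in the Tardieu R2 − R1 angle with change in VO2.** With one pair of changes per child this is a between-child correlation. It is still uncontrolled, it uses an unblinded manual measure, and at n = 15 it needs |r| above 0.51 for p < 0.05. It could lend false causal support.

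A practice walk or a repeat baseline would lessen familiarisation and regression, at the cost of extra testing. Neither would justify the efficacy wording.

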### *Subject Visits:*

- **Baseline:** Consent, Modified Ashworth Scale, modified Tardieu Scale, CP Quality of Life Questionnaire for Children/Adolescents, 6 minute walk with VO2 and gait analysis
- **Treatment:** SEMLC treatment

- **4 week follow-up:** Modified Ashworth Scale, modified Tardieu Scale, CP Quality of Life Questionnaire for Children/Adolescents, 6 minute walk with VO2 and gait analysis
- **12 week follow-up:** Modified Ashworth Scale, modified Tardieu Scale, CP Quality of Life Questionnaire for Children/Adolescents, 6 minute walk with VO2 and gait analysis

## 2.1 Participants

All subjects will be recruited from [name] Physical Medicine & Rehabilitation clinic. [name] will approach eligible patients and their parents in order to explain the study and to determine interest. A researcher of the study team will email and/or telephone call eligible participants on behalf of [name] and with her permission to inform the parents of the eligible participant of the study.

Inclusion Criteria:

- Age: 5-17 years. *Must be <18 prior to injection.*
- >10 kilograms at screening and injection visits
- Diagnosis of spastic diplegia OR mild- to moderate spastic quadriplegia Cerebral Palsy
- Gross Motor Function Classification System level: I, II, III
- Ability to ambulate independently without aid, equinus gait
- Absent of joint or bone deformities
- Eligible to receive SEMLC
- Cooperative and tolerant to testing procedures during clinic screening
- Presence of spasticity in one or both legs
- Be on a stable dose and regimen if on any prescribed medication/s
- Parent must have signed written informed consent and the Patient Authorization for Use and Release of Health and Research Study Information

Exclusion Criteria:

- Ankle contractures no more than -10 degrees with the knee extended
- Hemiplegia
- Wheelchair dependent
- Received Botulinum toxin within previous 4 months
- Uncontrolled epilepsy or certain types of seizures
- Fracture in the study limb within previous 12 months
- Infection or skin disorder at planned injection site
- Shortness of breath or other respiratory issues
- Uncontrolled clinically significant medical condition
- Received phenol or alcohol block in the study limb within previous 6 months
- Surgery in the study limb within previous 12 months
- Serial casting within previous 12 months
- New physiotherapy and/or orthotic regimen <1 month before study start. (physiotherapy and/or orthotic regimen will be permitted if it began >1 month before study start and maintained throughout study)

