#### (4 Weeks Post Treatment)

All procedures during the 4 weeks post treatment will mimic those conducted during the baseline visit (i.e., Modified Ashworth Scale, Modified Tardieu Scale, range of motion, CP QOL, gait analysis, 6MWT with oxygen consumption).

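### The GMFCS question covers all 15 children, but those already at level I cannot show the hypothesised decrease, and no visit lists a GMFCS assessment

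*Combined protocol and SAP*

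**What the plan says.** The inclusion criteria in 2.1 Participants accept "Gross Motor Function Classification System level: I, II, III". They set no cap on level I and no minimum number at level II or III. Another criterion in the same list is "Ability to ambulate independently without aid, equinus gait".

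Section 2.2 Outcome Measures poses the secondary question: "Does SEMLC have an effect on the Gross Motor Functional Classification System (GMFCS) classification in 15 children diagnosed with CP". Its hypothesis is that "SEMLC will decrease a child's GMFCS classification due to increased physical function", which fixes the direction: a lower level means better function. Fifteen is the full planned enrolment given in 2. DESIGN.

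Nothing in the document says how children at level I enter this question, and no summary measure, test or denominator is named for GMFCS. The procedures at 4 weeks are listed as "Modified Ashworth Scale, Modified Tardieu Scale, range of motion, CP QOL, gait analysis, 6MWT with oxygen consumption". The 12-week list is the same. GMFCS is absent from both, from the baseline assessments in 2.3 Procedures and from the list of subject visits in 2. DESIGN.

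**The concern.** The question is put to a group in which some members may be unable to move in the hypothesised direction. A child who enters at level I can be recorded only as unchanged or worse, however well the treatment works. The result for the whole group then depends partly on how many level I children happen to be recruited, and the plan leaves that number open.

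The study is described thus: "This study is a single center, open label study". No control group is described, so the GMFCS answer rests on change within each child. With so few children, a handful at level I changes the largest result that could be seen. If the denominator is not fixed beforehand, it may also be chosen after the data are known.

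**Working it through.** The plan gives no GMFCS figure, test, alpha or power, so there is no stated number to reproduce.

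**Inputs from the document.** Planned enrolment is 15 (2. DESIGN). Levels I to III are eligible (2.1). The hypothesised change is a decrease (2.2).

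**Inputs assumed.** The number at level I, k, is not given; I take 0, 3, 5, 8 and 10. The chance p that a level II or III child improves by at least one level is also not given; I use 30% for the estimate and 40% and 50% for the test. Level I children are taken to stay at level I.

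**Step 1: ceiling and dilution.** Only 15 − k children can decrease.

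- Highest possible improvement rate over all 15 = (15 − k)/15
- Expected rate over all 15 = p × (15 − k)/15

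| k at level I | Able to decrease | Ceiling over 15 | A 30% rate appears as |
|---|---|---|---|
| 0 | 15 | 100% | 30% |
| 3 | 12 | 80% | 24% |
| 5 | 10 | 67% | 20% |
| 8 | 7 | 47% | 14% |
| 10 | 5 | 33% | 10% |

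For k = 5, for example: 10/15 = 67%, and 0.30 × 10/15 = 20%. The mean change in level over all 15 shrinks by the same factor, because each unchanged level I child adds a zero.

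**Step 2: a test that drops ties.** In a sign test, unchanged children leave the analysis, so there is no dilution; at most 15 − k children can contribute an improvement. Take an exact two-sided test at 0.05 with nobody worsening. Five improvements give 2 × 0.5^5 = 0.0625, and six give 2 × 0.5^6 = 0.031, so at least six are needed. Power is P(X ≥ 6) with X binomial(15 − k, p).

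| k at level I | Power, p = 40% | Power, p = 50% |
|---|---|---|
| 0 | 0.597 | 0.849 |
| 3 | 0.335 | 0.613 |
| 5 | 0.166 | 0.377 |
| 8 | 0.019 | 0.062 |
| 10 | 0 | 0 |

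At k = 10 only five children can improve, so six improvements are impossible. The plan names no test; this one only shows where the loss goes when ties are dropped.

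**Step 3: can the change be measured?** Applying the eligibility criterion requires a level at entry. No later visit lists a classification, so a change could not be calculated for any child from the schedule as written.

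**The case against.** The strongest reply is that the plan specifies no GMFCS analysis, so no defined estimate exists to be diluted. The phrase about 15 children also appears in the primary, walking-distance and balance questions and may be stock wording, while the hypothesis speaks of an individual child. The numbers at level I are assumed; if few such children enrol, the effect is small. All of this stands, and it limits the weight of the point. It does not remove the gap, because no passage says how level I children are to be treated.

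Four stronger readings are tempting, and the document supports none of them.

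- **That the eligibility rule is wrong.** Level I children remain informative for oxygen consumption, walking distance, gait and spasticity. The defect is in how 2.2 frames one question.
- **That level I children pull the result toward harm.** A stable level I child contributes zero. A shift toward harm needs actual worsening or misclassification, and nothing in the plan points to either.
- **That level I enrolment is what makes a null GMFCS result unreadable.** In a study of 15 children with no control group described and no stated power, a null result would be hard to read anyway. Walking distance and gait also bear on function.
- **That enrolment will lean toward level I.** Requiring independent walking without an aid favours better-functioning children, but 2.3 Procedures allows gait aids during testing and no expected mix is given.

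**Conclusion.** The point holds as a minor one. Children at level I are eligible, are covered by the GMFCS question as worded, and cannot show the decrease it hypothesises. This follows from 2.1 and 2.2 alone and needs no assumption about the mix.

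Its size does depend on the mix. With one fifth to about half of the children at level I (3 to 8 of 15), the ceiling on the improvement rate falls to between 80% and 47%. Under a tie-dropping test the loss is in effective sample, and the power figures hold only for the assumed improvement rates with nobody worsening.

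The missing GMFCS assessment is the more basic gap: restating the question would not help if the level is never recorded again. The two need correcting together. The primary question is unaffected.

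**What to change.** - Keep levels I to III eligible.
- In 2.2, restate the GMFCS question as change among children at level II or III at baseline. Report the numbers improved, unchanged and worsened at each follow-up visit. Worsening must be shown for this group too, because counting only improvers in an uncontrolled before-after comparison would favour a positive answer, including one produced by classification error.
- Report level I children separately as maintained or worsened.
- Drop the reference to 15 children from this question.
- Add GMFCS to the baseline, 4-week and 12-week lists in 2. DESIGN and 2.3 Procedures.

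The cost is a smaller, openly stated denominator for one secondary outcome, and one classification per child per visit: at most 15 × 3 = 45, of which the baseline ones are already needed to apply the eligibility criterion. Recruitment, treatment and the primary analysis do not change.
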